5.5.6 Permitted dose adjustments and interruptions of study treatment

In case of suspected infusion reaction, the infusion can be stopped for 30 minutes and the patient observed to determine the severity of the reaction. Depending on the assessment of the patient, symptomatic treatment can be administered and the infusion can be restarted at a reduced rate if necessary.

These changes must be recorded on the Dosage Administration Record CRF.

5.5.7 Recommended treatment of adverse events

Potential adverse events should be treated symptomatically.

Intravenous administration of mAbs can be associated with infusion reactions secondary to hypersensitivity, Commercially Confidential Information. Most infusion reactions occur within the first 2 hours of mAb exposure. In this study, VAY736 will be infused over a 2 hour period. During this period, administration of VAY736 can be modified and clinical treatment provided as determined by the treating physician on a case-by-case basis. The following guidelines are provided using the National Cancer Institute Common Toxicity Criteria for allergic reaction, anaphylaxis and cytokine release [NCI-CTCAE/v4.03, Reference <http://evs.nci.nih.gov/ftp1/CTCAE/About.html>].

In the case of a suspected infusion reaction, the infusion can be stopped for 30 minutes and the patient observed to determine the severity of the reaction. Depending on the assessment of the patient, medication can be administered and the infusion can be restarted at a reduced rate if necessary. Additional guidance on severity grading and treatment includes the following:

- Mild National Cancer Institute (NCI) grade 1 infusion reactions do not require treatment.
- In case of moderate NCI grade 2 infusion reactions requiring symptomatic treatment, the patient can be treated with anti-histamines, NSAIDs, paracetamol/acetaminophen, intravenous fluids) as determined by the investigator, but only while adhering strictly to the maximal daily dose limits of these medications. The infusion can be stopped for 15 minutes and then restarted at a reduced rate.
- In case of more severe NCI grade 3 or 4 reactions, the infusion should be stopped and corticosteroids according to local guidelines administered intravenously.
- Other available medications at the bedside should include paracetamol/acetaminophen, adrenaline, bronchodilators, and /intravenous preparations of anti-histamines.

Infusion reactions of severity NCI grade ≥ 2 despite pre-medication with paracetamol/acetaminophen and an H1 blocker may require modification of the pre-treatment regimen. Medication to prevent or treat the signs and symptoms of infusion-related reactions will be provided by the study site.

Plasmapheresis may be helpful in situations in which decreasing the systemic concentration of VAY736 may be of clinical benefit, based on capacity of plasmapheresis to remove IgG antibody, such as the IgG monoclonal antibody VAY736, from intra- and extra-vascular compartments.

In the case of severe neutropenia requiring treatment, filgrastim (granulocyte colony-stimulating factor analog; G-CSF) may be used to stimulate the proliferation and differentiation of granulocytes.

In the case of clinically relevant hypogammaglobulinemia, an intervention may be required such as replacement by Intravenous Immunoglobulin (IVIG).

Medication used to treat AEs must be recorded on the Concomitant medications/Significant non-drug therapies (e)CRF.

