4.2 Exclusion criteria

All patients

Patients fulfilling **any** of the following criteria are not eligible for inclusion in this study:

1. Use of other investigational drugs at the time of Screening, or within 30 days or 5 half-lives of Screening, whichever is longer; or longer if required by local regulations.
2. Known hypersensitivity to any constituents of the study drug, to murine, chimeric or human antibodies, or to drugs of similar chemical classes (e.g., IgG1 biologics). Also, known hypersensitivity to study drug premedication (paracetamol (or acetaminophen) and H1 receptor blocker).
3. Prior use in the 12 months prior to Screening of any B-cell depleting therapy e.g., rituximab or other anti-CD20 mAb, anti-CD22 mAb, anti-CD52 mAb (patients B cell levels should also have returned to normal, if results are not available, a FACS sample should be taken at screening to confirm).
4. Use of prednisone or other systemic steroids for conditions other than pemphigus vulgaris within the 1 month prior to Baseline.
5. Use of topical steroids (or other topical treatment for PV) within 2 weeks prior to Baseline.
6. Recent previous treatment with phototherapy, biological therapy, immunosuppressive agents such as azathioprine (unless it is used as SoC medications for PV treatment as per inclusion criteria # 5), dapsone, or methotrexate. The following washout period will be required for such patients to be eligible to participate in the trial:
 - 6 months washout prior to Screening for IVIg, plasmapheresis, immunoadsorption or i.v. or oral cyclophosphamide;
 - 3 months washout prior to Screening for etanercept, adalimumab, ustekinumab, infliximab or any other immunologically active biologic therapy;
 - 1 month washout prior to Screening for UVB/PUVA therapy, dapsone, methotrexate, and any systemic immunosuppressants or other systemic treatment for PV.

Note: If taking consistent stable dose(s) of allowable standard-of-care (SoC) medications, these are allowable if dose /regimen is maintained throughout the study (refer to [Section 4.1](#) inclusion criterion #5).

Decisions about management of previous treatments are left to the treating physician in line with the patients' choices, and should be conducted according to local standard of care best practice. The present protocol does not support stopping a medication if the sole purpose is to allow a patient to then become eligible to enter the study.

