5.5.8 Rescue medication

Except the patient's Standard of Care treatment (SoC; oral corticosteroid +/- adjuvant therapy) described in [Section 5.5.5](#), no additional rescue medication is allowed; however, adjustment to a patient's SoC is allowable, with certain conditions, for a patient to remain on study.

During the Double-blind period (Weeks 0 to 24), adjustment of SoC is limited to one (1) increase (either corticosteroid or adjuvant therapy alone or both on the same day) in the first 24 weeks if the IGA score worsens by 1 point or more. With one increase, a patient can continue on the study without change to the study visit schedule.

If a patient has already had an increase in oral corticosteroid or in adjuvant immunosuppressive drugs (azathioprine or mycophenolate mofetil) and is still experiencing a disease flare up that in the Investigator's opinion requires intervention (e.g., IGA score worsens by a further 1 point or more from the prior SoC increase timepoint), then depending on when this second increase of SoC happens the patient should follow the schedule below:

- Second increase in SoC up to & including Week 12 – Patient to return and complete visits up to & including the Week 12 visit. Treatment to be unblinded early at the Week 12 visit.
- Second increase in SoC after Week 12 – Patient to return and skip forward to complete the Week 24 visit assessments. Treatment to be unblinded early (at the time of SoC increase or at the Week 24 visit).

Following this early unblinding, a patient on placebo is to be offered the opportunity of open label VAY736, whereas a patient on VAY736 would enter the long-term follow-up period (from Week 32 onwards). Similarly, if a patient previously on placebo prefers not to receive open label active treatment, they are to return within 4 weeks for their EoS visit

Commercially Confidential Information

If more than two increases of SoC treatment are required in an aim to control a patient's disease symptoms, such a patient will already have been withdrawn from the double-blind period and skipped forward to be monitored in the long-term follow up period following the second increase in SoC. Such patients would already have had their treatment unblinded after the second increase. These patients should continue to return for the visits/assessments in the long-term follow up period (from Week 32 onwards).

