5.5.10 Prohibited treatment

Use of the treatments displayed in the table below is NOT allowed after screening.

If, nevertheless, any of the below mentioned medication is taken during the study, a patient has either to be withdrawn from the study in case they are in the double-blind part or can stay in the study if they stop immediately the medication if such medication(s) have a short half-life or a minimal impact if taken punctually (see [Table 5-3](#)).

Commercially Confidential Information

Table 5-3 Prohibited treatment

Medication	Action
IVIg, plasmapheresis	Withdraw from double-blind period, unblind treatment and follow-up for safety
I.V. or oral cyclophosphamide	Withdraw from double-blind period, unblind treatment and follow-up for safety
Rituximab	Withdraw, unblind treatment and follow-up for safety. If taken after Week 24, patient should go directly to EOS visit.
Etanercept, adalimumab, ustekinumab, infliximab or any other immunologically active biologic therapy	Withdraw from double-blind period, unblind treatment and follow-up for safety
UVB/PUVA therapy	Discontinue phototherapy
Azathioprine, mycophenolate mofetil (if not part of SoC medication from Screening), dapsone, methotrexate, and any systemic immunosuppressants or immunomodulators	Discontinue medication
topical corticosteroids	Discontinue medication
topical calcineurin inhibitors (e.g., elidel)	

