Patients who withdraw prior to Week 12 should return for the Week 12 visit before skipping forward to enter the long term follow up period. Patients who withdraw after the Week 12 visit yet prior to Week 24 should return for the Week 24 visit before entering the long term follow up period (after Week 24). During the long term follow up period, patients will have visits according to the following schedule

until up to 2 years after last dose, Commercially Confidential Information unless the patient starts another immunomodulatory or immunosuppressive treatment:

- Every 8 weeks until the Week 40 visit
- A Week 52 visit
- Every 24 weeks until Week 100 visit

Commercially Confidential Information

The End of Study visit will include study completion evaluations followed by discharge from the study.

Patients who withdraw after Week 24, during the long term safety follow up period, will be asked to return and complete the end of study visit. Commercially Confidential Information

Commercially Confidential Information

For subjects who are lost to follow-up (i.e. those subjects whose status is unclear because they fail to appear for study visits without stating an intention to withdraw), the investigator should show "due diligence" by documenting in the source documents steps taken to contact the subject, e.g. dates of telephone calls, registered letters, etc.

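### IVIG and plasmapheresis are named as adverse-event treatments in Protocol 5.5.7 but prohibited in 5.5.10, and Table 5-3 orders unblinding without saying when, so the Week 12 PDAI could be scored with the code broken

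*Protocol*

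**What the plan says.** Protocol 5.5.7 (recommended treatment of adverse events) offers plasmapheresis: "Plasmapheresis may be helpful in situations in which decreasing the systemic concentration of VAY736 may be of clinical benefit". Section 3.6.2.2.2, on infusion reactions, makes the same suggestion. For low immunoglobulins, 5.5.7 says: "In the case of clinically relevant hypogammaglobulinemia, an intervention may be required such as replacement by Intravenous Immunoglobulin (IVIG").

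Protocol 5.5.10 (prohibited treatment) says: "Use of the treatments displayed in the table below is NOT allowed after screening". If a listed treatment is taken anyway, "a patient has either to be withdrawn from the study in case they are in the double-blind part", or may stay after stopping a product that is short-lived or has minimal impact. The Table 5-3 row for IVIg and plasmapheresis reads: "Withdraw from double-blind period, unblind treatment and follow-up for safety". Exclusion criterion 6 in 4.2 also treats both as relevant prior therapy: "6 months washout prior to Screening for IVIg, plasmapheresis, immunoadsorption or i.v. or oral cyclophosphamide".

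On unblinding, 5.5.8 covers a second increase in standard of care up to Week 12. The patient completes visits through Week 12, and then: "Treatment to be unblinded early at the Week 12 visit". Section 5.4 provides for unblinding after Week 24, or earlier under 5.5.8. It limits any further unblinding to emergencies, the interim analysis and the end of the study. Event 5 in Appendix 4 is single-patient unblinding after Week 24, or at Week 12 under 5.5.8. Neither list mentions Table 5-3.

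On follow-up, 5.5.11 says: "Patients who withdraw prior to Week 12 should return for the Week 12 visit". Section 6.4.1 has the investigator score the PDAI, and 9.1 keeps every dosed subject in the full analysis set.

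**The concern.** Two problems follow.

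First, the same treatment is both suggested and prohibited, and neither section refers to the other. An investigator who acts on 5.5.7 breaches 5.5.10, and nothing visible says what should happen to a patient treated for an adverse event rather than for pemphigus. Sites may handle the same event differently.

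Second, the instruction to unblind has no timing. If the code is broken on the day of treatment and the patient then returns for Week 12, a treating investigator who knows the assignment scores the primary endpoint. That score may also reflect the added treatment. The protocol describes pemphigus as caused by autoreactive antibodies, says that plasmapheresis removes IgG, and requires a six-month washout for both therapies. Plasmapheresis would remove study drug as well, so the direction of any effect cannot be fixed in advance. The visible parts of the protocol and of SAP 7.1.3 do not say how such PDAI values are handled, and SAP 7.1.4 lists supportive analyses as not applicable.

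**Working it through.** **Passages side by side**

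| Question | 5.5.7 / 3.6.2.2.2 | 5.5.10 / Table 5-3 | 5.4, 5.5.8, Appendix 4 |
|---|---|---|---|
| May IVIG or plasmapheresis be given after dosing? | Named as options | Not allowed after screening | Not addressed |
| Does the patient stay in the double-blind period? | Silent | No | Not addressed for this event |
| When is the code broken? | Silent | Ordered, no time given | Week 24; Week 12 or later under 5.5.8; emergency |

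The first row is a contradiction. The third is a gap: Table 5-3 creates an unblinding event that the lists of permitted unblinding do not contain. Add the 5.5.11 return visit and the investigator-scored PDAI, and an unblinded Week 12 primary value is possible under the text as written.

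**The plan's own figures**

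Inputs: SD 8, with 9 VAY736 and 6 placebo patients (Protocol 9.6). Criteria (synopsis, data analysis): 50% posterior probability of a difference of at least 10 points, and 90% of a difference above zero, with non-informative normal priors.

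- SE = 8 × √(1/9 + 1/6) = 4.216.
- The first criterion needs an observed difference of at least 10. The second needs 1.2816 × 4.216 = 5.40. The first therefore decides.
- Chance of success at true difference d = 1 − Φ((10 − d)/4.216).
- d = 0: 0.89% (stated: below 1%). d = 6: 17.1% (stated: below 20% for differences under 6). d = 14: 82.9% (stated: approximately 80%).

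The stated figures reproduce, allowing for rounding in the last.

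**One affected patient**

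The documents give neither the frequency of use nor the size of any shift. Assume that one Week 12 PDAI in an arm of nine shifts by 10 to 20 points.

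- Share of the arm: 1/9 = 11%.
- Shift in the arm mean: 10/9 = 1.1 to 20/9 = 2.2 points, against the 10-point criterion.
- Shift in favour of VAY736, d = 0: 1 − Φ((10 − 1.11)/4.216) = 1.75%, to 1 − Φ((10 − 2.22)/4.216) = 3.25%.
- Shift against VAY736, d = 14: Φ((4 − 1.11)/4.216) = 75%, to Φ((4 − 2.22)/4.216) = 66%.

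**One value left out**

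With 8 against 6, SE = 8 × √(1/8 + 1/6) = 4.320. The chance of success is 1.03% at d = 0 and 82.3% at d = 14. Losing one value costs little precision; a biased value matters more than a missing one.

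These results are conditional on a case occurring before Week 12. They do not estimate how likely that is.

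**The case against.** The strongest reply is that the passages can be read in sequence: 5.5.7 is permissive and silent on disposition, and 5.5.10 sets the consequence if a listed treatment is given. A patient could be treated and then withdrawn, and 11.1 allows immediate safety action even as a deviation. This stands in part. It would be wrong to say that 5.5.7 tells sites to keep the patient. But a treatment that one section suggests and another prohibits still needs a linking rule, and section 11 permits no authorised deviations.

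A reader might infer that the rule selectively removes or unblinds VAY736 patients. The documents do not show this:

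- Table 5-3 applies to every arm, and treating staff are blinded, so a placebo patient could also be treated.
- Nothing visible ties hypogammaglobulinemia to VAY736 alone; all patients take corticosteroids, some with azathioprine or mycophenolate.
- The only visible scheduled immunoglobulin tests start at Week 76. IVIG prompted by them would come after the Week 24 unblinding.
- Section 3.6.2.2.2 reports only mild-to-moderate infusion reactions to single VAY736 doses up to 10 mg/kg.
- The Week 12 visit is still requested, and dosed patients stay in the full analysis set, so they are not removed from the primary analysis.

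It can also be argued that 5.4 and Appendix 4 already imply holding the blind to Week 12. That is a reasonable reading, but neither mentions Table 5-3, so an unblinded Week 12 score is possible, not certain. Finally, text is blacked out in 5.5.10 before Table 5-3 and in the analysis-set and primary-analysis sections. An exception or handling rule may exist there. Section 9.4.3 also commits to checking the missing-at-random assumption at blinded review, with further methods if needed.

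**Conclusion.** The conflict between 5.5.7 (with 3.6.2.2.2 for plasmapheresis) and 5.5.10 with Table 5-3 is real in the visible text and must be reconciled. The untimed code break is also real: it does not fit 5.4, 5.5.8 or Appendix 4, and it leaves open an unblinded score of the primary endpoint. An effect falling mainly on VAY736 patients is plausible, most clearly for plasmapheresis given to lower drug levels, but it is not established.

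The frequency before Week 12 is unknown and probably low. If one case occurred, the arm mean would move by 1.1 to 2.2 points, resting wholly on the assumed 10 to 20 point shift in an arm of nine. That would be enough to take the false-positive chance above the stated 1%, or to lower the chance of success at a true difference of 14 from 82.9% to between 75% and 66%. This should be corrected because the correction is cheap; it does not undermine the design.

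**What to change.** 1. The sponsor should reconcile 5.5.7, 3.6.2.2.2, 5.5.10 and Table 5-3, and state what happens to a patient who receives IVIG or plasmapheresis for an adverse event, as distinct from use for pemphigus. Whether and when to use either treatment, and the resulting disposition, are clinical decisions on which this review takes no position.
2. Align the code-break timing in Table 5-3 with 5.4, 5.5.8 and Appendix 4. For a patient who leaves the double-blind period before Week 12, the Week 12 PDAI, IGA and ABSIS should be scored before the code is broken. Emergency unblinding under 5.5.12 stays as it is. Add the Table 5-3 event to the lists in 5.4 and Appendix 4.
3. In the SAP, flag PDAI values recorded after IVIG or plasmapheresis, and repeat the Week 12 comparison without them as a sensitivity analysis.

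The cost is a wording amendment and one extra analysis. A few patients may learn their assignment later than they otherwise would.

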5.5.8 Rescue medication

Except the patient's Standard of Care treatment (SoC; oral corticosteroid +/- adjuvant therapy) described in [Section 5.5.5](#), no additional rescue medication is allowed; however, adjustment to a patient's SoC is allowable, with certain conditions, for a patient to remain on study.

During the Double-blind period (Weeks 0 to 24), adjustment of SoC is limited to one (1) increase (either corticosteroid or adjuvant therapy alone or both on the same day) in the first 24 weeks if the IGA score worsens by 1 point or more. With one increase, a patient can continue on the study without change to the study visit schedule.

If a patient has already had an increase in oral corticosteroid or in adjuvant immunosuppressive drugs (azathioprine or mycophenolate mofetil) and is still experiencing a disease flare up that in the Investigator's opinion requires intervention (e.g., IGA score worsens by a further 1 point or more from the prior SoC increase timepoint), then depending on when this second increase of SoC happens the patient should follow the schedule below:

- Second increase in SoC up to & including Week 12 – Patient to return and complete visits up to & including the Week 12 visit. Treatment to be unblinded early at the Week 12 visit.
- Second increase in SoC after Week 12 – Patient to return and skip forward to complete the Week 24 visit assessments. Treatment to be unblinded early (at the time of SoC increase or at the Week 24 visit).

Following this early unblinding, a patient on placebo is to be offered the opportunity of open label VAY736, whereas a patient on VAY736 would enter the long-term follow-up period (from Week 32 onwards). Similarly, if a patient previously on placebo prefers not to receive open label active treatment, they are to return within 4 weeks for their EoS visit

Commercially Confidential Information

If more than two increases of SoC treatment are required in an aim to control a patient's disease symptoms, such a patient will already have been withdrawn from the double-blind period and skipped forward to be monitored in the long-term follow up period following the second increase in SoC. Such patients would already have had their treatment unblinded after the second increase. These patients should continue to return for the visits/assessments in the long-term follow up period (from Week 32 onwards).

For all patients, regardless of any increase(s) to SoC treatment(s), the duration of the long-term follow up and determining when End of Study (EoS) takes place is to follow the decision tree in [Appendix 5](#).

If worsening occurs in-between visits – the investigator or study staff are to request the patient return to the site for an ad-hoc unplanned visit to be evaluated; alternatively, for corticosteroid dose adjustment only, consultation over the phone is also possible.

SoC dose and any failure of a patient to progress in their taper will be captured at every visit in the (e)CRF.

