4.1 Inclusion criteria

All patients

Patients eligible for inclusion in this study have to fulfill **all** of the following criteria:

1. Written informed consent must be obtained before any assessment is performed.
2. Male and female patients 20 to 70 years of age inclusive (at the time of the Screening visit), and having passed Screening examinations by past medical history, physical examination, vital signs, electrocardiogram, and laboratory tests.
3. Diagnosis of PV according to (i) presence of blisters or erosions of the skin or mucous membranes, plus (ii) characteristic documented histological findings in the skin, plus (iii) characteristic findings from direct immunofluorescence in skin

Commercially Confidential Information

If results are not available, biopsies and a blood sample have to be taken at screening to confirm diagnosis.

4. Presence of mild to moderate active PV at Baseline as defined by a PDAI score between 20 and 60 (inclusive) or for a PDAI below 20: an IGA of 2 to 3 (e.g., at least 1% but not more than 10 % BSA involvement).

5. On a stable dose(s) of oral corticosteroid +/- adjuvant therapy of azathioprine or mycophenolate mofetil. Requirements for these standard-of-care (SoC) medications are:
 - Oral corticosteroids alone, with steroid dose to be equivalent to prednisone ≥ 15 mg per day but no greater than 2 mg/kg/day; or
 - Oral corticosteroid + azathioprine, with steroid dose to be equivalent to prednisone ≥ 2.5 mg per day but no greater than 1 mg/kg/day, and azathioprine with no specific daily dose requirement; or
 - Oral corticosteroid + mycophenolate mofetil, with steroid dose to be equivalent to prednisone ≥ 2.5 mg per day but no greater than 1 mg/kg/day, and mycophenolate mofetil with no specific daily dose requirement.
6. SoC medications considered stable if the daily dose has not changed within the 7 days preceding the day of dosing (Day 1) for oral corticosteroid, or within the 14 days preceding the day of dosing (Day 1) for azathioprine and mycophenolate mofetil. Patients must weigh in the range of 40 kg to 150 kg inclusive.
7. Able to communicate well with the investigator, to understand and comply with the requirements of the study.

Open-label patients (i.e. for placebo-treated patients)

1. Presence of mild to moderate active PV at unblinding, as defined by a PDAI score more than 10.

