6.4.3 Investigator global assessment (IGA)

An IGA score on a 0-4 scale will be used to assess each patient's PV disease activity as per the scale in [Section 21-Appendix 9](#) (modified from [Mahajan et al 2005](#)). IGA scores will be captured in the eCRF.

For the IGA, active PV lesions are defined as urticarial lesions, blisters and erosions which are not epithelialized. Erythematous patches and erosions which have healed to the extent that they are epithelialized are not included in the body surface area assessment (BSA). For the estimation of BSA, the palm of the patient (not including the surface of the fingers) is considered to be 0.5% of the total BSA ([Agarwal and Sahu 2010](#)).

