1	in one quadrant		1	present																											
2	two quadrants																														
3	three quadrants																														
4	affects whole skull																														
10	at least one lesion >6 cm																														
Total Scalp	/10	/1																													

Mucous membrane

Anatomical location	Erosion/Blister	
	0 absent 1 1 lesions 2 2-3 lesions 5 >3 lesions or 2 lesions >2 cm 10 entire area	Number lesions if ≤3
Eyes		
Nose		
Buccal mucosa		
Hard palate		
Soft palate		
Upper gingiva		
Lower gingiva		
Tongue		
Floor of mouth		
Labial bucosa		
Posterior pharynx		
Anogenital		
Total Mucosa	/120	

Total Activity Score

= Total Skin Activity Score + Total Scalp Activity Score + Total Mucosa Activity Score

[figure not shown]
Total Damage Score

= Total Skin Damage Score + Total Scalp Damage Score

PDAI Score

= Total Activity Score + Total Damage Score

19 Appendix 7: Assessment of Body Surface Area

Head & neck:	9%	Arm incl hand:	9%
Trunk (front & back)	36%	Leg:	18%
Genitals:	1%	Palm of the hand (including fingers):	1%

20 Appendix 8: ABSIS scoring sheet

ABSIS SCORING SHEET

Date: _____
Patient's weight
(kg): _____

Skin Involvement (Max BSA)	Patient's BSA	Weighting Factor	% BSA x Weighting Factor
Head & neck (9%)			
L Arm including hand (9%)			
R Arm including hand (9%)			
Trunk (front & back) (36%)			
L Leg (18%)			
R Leg (18%)			
Genitals (1%)			
			Total Score ¹ _____

¹Skin Involvement Total Score ranges from 0 – 150 points

Legend for weighting factor (most dominant appearance of skin lesions):	
1.5	Erosive, exudative lesions
1.0	Erosive, dry lesions
0.5	Reepithelialized lesions (incl. post inflammatory erythema and/or hyperpigmentation)

I. Oral Extent (enter 1 for presence of lesions, 0 absence of any lesion):

Upper gingival mucosa	
Lower gingival mucosa	
Upper lip mucosa	
Lower lip mucosa	
Left buccal mucosa	
Right buccal mucosa	
Tongue	
Floor of the mouth	
Hard palate	
Soft palate	
Pharynx	
	Total Score ² _____

²Oral Total Score ranges from 0-11

II. **Severity** (Subject discomfort during eating/drinking)

Food, e.g.	Level	Factor of Discomfort	Level x Factor of Discomfort
Water	1		
Soup	2		
Yogurt	3		
Custard	4		
Mashed potatoes/scrambled egg	5		
Baked fish	6		
White bread	7		
Apple/ raw carrot	8		
Fried steak/ whole-grain bread	9		
			Total Score ³ _____

³Total Severity Score ranges from 0-45

Legend for Factor of Discomfort	
1	Pain/bleeding occurred always

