0.5	Pain/bleeding occurred sometimes
0	Never experienced problems

ABSIS Score

= Total Skin Involvement Score + Total Oral Score + Total Severity Score (Food)

21 Appendix 9: IGA Scale

Score	Cutaneous disease	Mucosal disease
 0 = Clear	No signs of active PV disease	No signs of active PV disease
 1 = Almost clear	<1% BSA affected by active PV lesions	Some erosions, but no difficulty in swallowing or chewing
 2 = Mild	1 to <3% BSA affected by active PV lesions	Buccal and gingivolabial mucosal involvement. Difficulty for solid food intake.
 3 = Moderate	3 to 10% BSA affected by active PV lesions	Extensive oral mucosal involvement. Difficulty for semisolid food intake.
 4 = Severe	>10% BSA affected by active PV lesions	Extensive oral mucosal involvement with other mucous membranes involved. Difficulty in swallowing liquids and any other food.

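### A patient who enters at IGA 4 and stays there cannot meet the 1-point worsening rule for a first standard-of-care increase, so worsening disease can be treated only off-rule or after withdrawal

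*Protocol*

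**What the plan says.** **Entry.** Protocol section 4.1, criterion 4, asks for mild to moderate active disease "as defined by a PDAI score between 20 and 60 (inclusive) or for a PDAI below 20: an IGA of 2 to 3". The IGA limit, with its example of 1 to 10% body surface area (BSA), belongs to the PDAI-below-20 route only. The synopsis says the same.

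**Scale.** Section 6.4.3: "An IGA score on a 0-4 scale will be used to assess each patient's PV disease activity". In Appendix 9 the top score, 4, is labelled severe. Its skin column reads ">10% BSA affected by active PV lesions"; its mucosal column begins "Extensive oral mucosal involvement with other mucous membranes involved".

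**First SoC increase.** Section 5.5.8 excludes any other rescue and limits SoC adjustment in the double-blind period to one increase "in the first 24 weeks if the IGA score worsens by 1 point or more". The consequence is mild: "With one increase, a patient can continue on the study without change to the study visit schedule".

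**Second SoC increase.** The standard here is looser. It applies to a patient who has already had an increase and "is still experiencing a disease flare up that in the Investigator's opinion requires intervention", with a further IGA rise given only as an example. This step leads to early unblinding and, for placebo patients, an offer of open-label VAY736.

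**The concern.** The first-increase rule uses a change on a bounded scale, and the entry criteria admit patients at its upper bound. For them the only stated trigger cannot fire, however far the disease spreads, unless the score first falls. These are the eligible patients with the highest IGA.

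Section 3.4 justifies the placebo arm partly on the ground that continuous SoC limits the risk of uncontrolled disease. A rule that gives no permitted first step to the patients with the highest IGA sits badly with that. It also leaves the site to choose between leaving SoC unchanged, deviating, and withdrawing the patient, and sites may choose differently.

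There is a smaller analytical stake. The synopsis says that the PDAI model may be adjusted for SoC increases, and that more increases on placebo might count as a sign of efficacy. For a patient held at IGA 4, whether an increase is recorded at all would depend on the site's willingness to go outside the rule.

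**Working it through.** The plan gives no figure to reproduce on this point. The check has four parts.

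**1. Can the condition be met from each starting score?** Scores w with w ≥ start + 1 and w ≤ 4:

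| Starting IGA | Scores that qualify |
|---|---|
| 0 | 1, 2, 3, 4 |
| 1 | 2, 3, 4 |
| 2 | 3, 4 |
| 3 | 4 |
| 4 | none |

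Section 5.5.8 does not say whether worsening is measured from baseline or from the previous visit. For a course of 4, 4, 4 the change is 0 on both readings.

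**2. Is IGA 4 compatible with PDAI 20 to 60?** Inputs are the scoring sheets in Appendices 6, 7 and 9.
- Whole trunk: chest, abdomen and back/buttocks at 10 each give 3 × 10 = 30. The trunk counts as 36% BSA, above the 10% cut-off.
- Smaller extent: just over 10% BSA spread over four regions is just over 2.5% each. If each region scores 5 to 10, the PDAI is 4 × 5 = 20 to 4 × 10 = 40.
- Mucosa: a site scores 5 for ">3 lesions or 2 lesions >2 cm". Eight oral sites at 5 give 40; one further mucosa at 1 to 10 gives 41 to 50. This example assumes that the mucosal column alone can set the IGA, which Appendix 9 does not state.

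**3. Does other visible text permit a first increase?**
- Section 3.1 (minimal adjustments) and section 5.5.5 (limited changes) hold SoC stable until disease control. Neither adds a permission to increase.
- The taper-failure increase in 5.5.5 needs disease control, then no new lesions and about 80% healing. It helps only a patient who has first improved clinically. A patient with very extensive disease might do so while still scoring 4.
- The paragraph in 5.5.8 on worsening between visits says how the patient is assessed and how a steroid dose may be adjusted. It does not lift the IGA condition.
- The investigator-opinion standard in 5.5.8 needs an earlier increase.
- Section 11 rules out authorized deviations. Section 11.1 expects immediate action for a patient's safety even when it deviates from the protocol.

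**4. What would be lost, and under what condition?**
- If the patient withdraws under section 5.5.11: there are 7 post-baseline PDAI visits (Weeks 3, 6, 9, 12, 16, 20, 24). Withdrawal before Week 3 loses 6 (all but Week 12); after Week 3, 5; after Week 6, 4; after Week 9, 3. After Week 12 it loses 2 (Weeks 16 and 20); after Week 16, 1; after Week 20, 0. Week 12, the primary time point, is kept throughout.
- If the site gives no increase at all and the patient stays in: unblinding is at Week 24. After a second increase by Week 12 it would be at Week 12, a gap of 24 − 12 = 12 weeks. For a later second increase the gap is between 0 and just under 12 weeks.
- If the site gives an off-rule increase: no visible text removes the patient or any visit.

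One patient would be 1/6 = 17% of planned placebo patients or 1/9 = 11% of an active arm.

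**The case against.** The strongest reply has five parts.

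*The target population is mild to moderate, and Appendix 9 calls IGA 4 severe.* This makes such patients an edge case, perhaps an empty one. It does not exclude them, because criterion 4 defines mild to moderate by the PDAI score and section 4 forbids investigators to add criteria.

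*Section 5.5.8 lets steroid be adjusted by phone when disease worsens between visits, and the IGA can hardly be scored by phone.* This is a real tension and suggests that the trigger was not meant as an absolute lock. But the text describes how an adjustment is made, not when an increase is allowed.

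*Part of 5.5.8 is blacked out and the Appendix 5 decision tree cannot be seen.* This stands. A provision may exist there, so the point concerns the readable text only.

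*An objective trigger protects a small PDAI comparison.* That is a good reason to keep it wherever it can work. From IGA 4 it cannot.

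*The consequences are small.* A reader might infer the opposite: that an IGA 4 patient who worsens must leave the double-blind period, lose visits and forgo early open-label drug. The documents do not support that. Table 5-3 does not list an off-trigger SoC increase, and 5.5.8 ties leaving the double-blind period to the second increase. The second-increase paragraph asks only whether an increase has already happened, so an urgent safety increase under section 11.1 would open that route. Section 5.5.8 does speak of conditions for staying on study, but it attaches no withdrawal action to a first increase. The visible cost of an off-rule increase is a recorded deviation.

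**Conclusion.** The gap is real in the visible text. An eligible patient who enters at IGA 4 and stays there has no rule-conforming first SoC increase in Weeks 0 to 24 unless they first improve enough to start, and then fail, the taper. If the disease worsens, the investigator must act outside the rule or after withdrawal. Treatment is not barred, and the losses counted in part 4 of the working arise only if the site withdraws the patient or gives no increase.

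The number affected cannot be derived from the documents and may be zero, and no effect on the primary analysis can be estimated. The conclusion assumes that the blacked-out part of 5.5.8 and Appendix 5 contain no provision for these patients. It is worth correcting because it concerns the safety of the eligible patients with the highest IGA and the repair is small. It does not threaten the trial's main result.

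**What to change.** Add one sentence to section 5.5.8: for a patient whose IGA is already 4, the first SoC increase is also permitted for a flare that the investigator judges to need intervention (for example new lesions or a rise in PDAI), and it counts as the first increase for the second-increase rule. This borrows the standard that 5.5.8 already applies to the second increase. Leave the 1-point trigger for all other patients, and the entry criteria, as they are.

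The cost is one sentence, made by written amendment as section 11.1 requires. No new assessment is needed, since PDAI and disease activity are already scored at scheduled visits. The downside is slightly more investigator discretion in these few patients. An added increase before Week 12 could also slightly reduce the PDAI difference between arms at Week 12.
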